3.8. Interim Analyses

An interim safety analysis is planned and will be conducted by an independent Data Monitoring Committee (DMC). The analysis will be based on a safety review when all subjects have completed at least 12 weeks of treatment. The safety analysis plan will be prepared separately.

3.9. CINRG Natural History Population

The largest prospective multicenter study of the natural history of DMD, performed by the Cooperative International Neuromuscular Research Group (CINRG), enrolled more than 400

ambulant and non-ambulant male patients with DMD and collected a comprehensive set of clinical measures over a 10-year period. In order to illustrate the clinical benefit of ataluren in subjects ≥ 2 and ≤ 5 years of age in Protocol PTC124-GD-030-DMD, subjects from the CINRG database will be selected based on ≥ 2 and ≤ 5 of age-match at study entry. Additional selection criteria (i.e. baseline TFTs, NSAA scores, etc.) maybe selected if significant differences in baseline demographics are observed between the CINRG cohort and the Study 030 population. The data extracted from the CINRG database will include demographics at study entry, and available Timed Function Test and North Star Ambulatory Assessment by the same time points: study entry, Weeks 28 and 52. The selected CINRG data will be summarized similarly to Study 030.

The data extracted from the CINRG database will not be included in study databases with the data collected in PTC124-GD-030-DMD. That is, the CINRG data will not be included in the SDTM and ADaM databases which support the tables, listings, and figures for the study CSR and will not be included in the study submission package.

Instead, the data from the CINRG database will exist as standalone SAS datasets. Separate ADaM datasets, tables, and listings will be generated to present results from the natural history CINRG database alongside results from PTC124-GD-030-DMD. These summaries will be kept separate from the study CSR.

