4.2. Inclusion Criteria

Patients must meet all of the following conditions to be eligible for enrollment into the study:

General inclusion criteria

1. Evidence of signed and dated informed consent document(s) indicating that the study candidate (and/or a parent/legal guardian) has been informed of all pertinent aspects of the study. *Note: As all study candidates are considered children under local regulation, at least one parent or legal guardian must provide written consent prior to initiation of study-related procedures, in accordance with local regulation, and the study candidate may be required to provide written assent. The rules of the responsible institutional review board/independent ethics committee (IRB/IEC) regarding whether one or both parents must provide consent and the appropriate ages for obtaining consent and assent from the patient should be followed.*
2. Males ≥ 2 to < 5 years of age
3. Body weight ≥ 12 kg
4. Willingness and ability to comply with scheduled visits, drug administration plan, study procedures, and study restrictions.
5. No clinically significant abnormality based upon laboratory assessments during the screening period, in the opinion of the Investigator; good general health, as determined during the screening period by medical history and physical examination (including vital sign measurements).

DMD inclusion criteria

6. Diagnosis of DMD based on an elevated serum CK and genotypic evidence of dystrophinopathy. *Medical documentation of phenotypic evidence of dystrophinopathy needs to be provided upon request by the PTC Therapeutics medical monitor.*
7. Documentation of the presence of a nonsense mutation in at least 1 allele of the dystrophin gene.
8. Verification that a blood sample has been drawn for sequencing of the dystrophin gene. *Note: A patient who has written documentation of a nonsense mutation as the cause of dystrophinopathy need not wait for confirmatory results to start study drug.*

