14.1.2. Inclusion of Minors

Inclusion of children ≥ 2 to < 5 years old in this protocol is appropriate and necessary. The benefit-risk ratio is enhanced by the known severity of the disease phenotype in patients with dystrophinopathy caused by nonsense mutations, the generally favorable safety profile of ataluren, and the limited population of patients with nonsense-mutation-mediated disease (~13% of the total dystrophinopathy population). Inclusion of young children will allow an understanding of how age-dependent disease characteristics may affect PK parameters and, therefore, dosing.

In standard toxicology studies, dosing is initiated in young adult rats (6 to 8 weeks old) and in 4- to 6-month old dogs. However, the chronic toxicology studies conducted with ataluren initiated dosing in weanling animals (approximately 4- to 5-week-old rats, and dogs < 3 months of age) to support dosing of pediatric subjects as young as 2 years of age. A detailed summary of methods and results of these chronic toxicity studies is provided in Section 7 of the Ataluren IB.

In the clinic, ataluren has previously been administered to patients as young as 3 years old. A Phase 2 study of ataluren in patients with methylmalonic acidemia (MMA) enrolled 11 patients, including 2 patients who were 3 years old and 1 patient who was 4 years old. All 3 of these patients completed the study as planned, receiving ataluren 5, 5, 10 mg/kg for 28 days in Cycle 1 and ataluren 10, 10, 20 mg/kg for 28 days in Cycle 2; there was a washout period of 21 days between the cycles.

Ataluren was well tolerated by the 3 patients < 6 years old in the MMA study. Treatment-emergent AEs in these patients were vomiting, pyrexia, nasopharyngitis, cough, flatulence, and rash. All treatment-emergent AEs were mild or moderate in severity, and none were serious or led to discontinuation of treatment. Overall, the ataluren safety profile was similar in patients < 6 years old and ≥ 6 years old.

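### The CINRG comparator is selected on age without prespecifying dystrophin mutation class, so a wholly nonsense-mutation trial may be shown beside mostly other genotypes, with an effect of unknown direction.

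*SAP*

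**What the plan says.** **The trial.** Protocol 4.2, inclusion criterion 7, requires "Documentation of the presence of a nonsense mutation in at least 1 allele of the dystrophin gene". Apart from any eligibility deviation, the Study 030 cohort is entirely nonsense mutation.

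**The comparator.** SAP 3.9 describes CINRG as a natural history study of more than 400 "ambulant and non-ambulant male patients with DMD and collected a comprehensive set of clinical measures over a 10-year period". It gives no mutation class. The selection rule is that "subjects from the CINRG database will be selected based on" age at entry, from 2 to 5 years inclusive.

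**Room for more criteria.** The same section adds: "Additional selection criteria (i.e. baseline TFTs, NSAA scores, etc.) maybe selected if significant differences in baseline demographics are observed". Mutation class is not among the examples.

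**The extract.** "The data extracted from the CINRG database will include demographics at study entry, and available Timed Function Test and North Star Ambulatory Assessment" at entry, Week 28 and Week 52. Genotype is not listed.

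**The purpose.** The section opens its rationale with "In order to illustrate the clinical benefit of ataluren in subjects" in this age group. The CINRG results are to be tabulated beside those of Study 030, in outputs held apart from the study report; the CINRG data also stay out of the submission package.

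**The concern.** Study 030 has no control arm, so CINRG is the only comparator that the SAP offers for the timed function tests and the NSAA. One cohort is defined by a specific class of mutation. The other is DMD in general, chosen on age. If untreated boys with nonsense mutations progress differently from other boys with DMD, the gap between the two sets of columns contains that difference as well as any drug effect.

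The listed data would not reveal the problem. The trigger for extra selection criteria is a difference in baseline demographics, and genotype is not named in what is to be extracted. As specified, the tables would carry no sign that the cohorts may differ in mutation class.

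Correcting the age window, matching on baseline function or adding treatment data would each leave this gap in place.

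**Working it through.** **1. Is mutation class specified anywhere for CINRG?** SAP 3.9 is the only section that defines the comparator. Set against the trial:

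| Item | Study 030 | CINRG comparator |
|---|---|---|
| Mutation class | Nonsense mutation required (Protocol 4.2) | Not a stated criterion |
| Mutation class in the data | Documented, with a confirmatory sequencing sample (Protocol 4.2, 8.2.6) | Not in the listed extract |

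Neither document supplies the missing item elsewhere.

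**2. The protocol's own share of nonsense mutations.** Protocol 1 gives about 13%; Protocol 2.2.1 gives 10-15%. Checked against the prevalences in Protocol 1 and 2.1:
- US: 0.13 × 13,000 = 1,690 (stated 1,700); in reverse, 1,700 / 13,000 = 13.1%.
- Europe: 0.13 × 17,000 = 2,210 (stated 2,200); in reverse, 2,200 / 17,000 = 12.9%.

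The 13% figure is reproduced.

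**3. Expected mismatch.** Assumption: CINRG boys in the age window have the general DMD mix. Share with another mutation class = 1 − p.
- p = 0.10: 90%
- p = 0.13: 87%
- p = 0.15: 85%

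In Study 030 the corresponding share is 0%.

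**4. How firm is the word mostly?** The number of age-eligible controls is not given, so two sizes are assumed.
- 12 controls: expected nonsense-mutation boys = 12 × p = 1.2 to 1.8.
- 30 controls: 30 × p = 3.0 to 4.5.

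With 12 controls, the binomial probability that more than half have another class is 0.995 at p = 0.15, 0.998 at p = 0.13 and 0.999 at p = 0.10. For most controls to be expected to have a nonsense mutation, CINRG's share would have to exceed 50%, more than three times the upper figure (0.50 / 0.15 = 3.3).

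**5. What a nonsense-mutation column could contain.** Taking 400 as the cohort size: 400 × 0.10 = 40, 400 × 0.13 = 52, 400 × 0.15 = 60. These counts cover all ages, and the age restriction will reduce them. To expect 12 such controls, the age-eligible pool must be 12 / p: 80 at 15%, 93 at 13%, 120 at 10%.

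**6. Effect on the outcomes.** Not calculable. Neither document gives timed-function or NSAA progression by mutation class, or names a test between the cohorts.

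**The case against.** **No document shows that course differs by mutation class.** This stands. The nearest text is in Protocol 14.1.2, which cites "the known severity of the disease phenotype in patients with dystrophinopathy caused by nonsense mutations" when arguing benefit and risk for enrolling young children. It calls the phenotype severe and does not compare it with other DMD mutations. It also speaks of dystrophinopathy, which is wider than DMD. It establishes neither that a bias exists nor its direction.

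**A reader might infer that the mismatch flatters ataluren.** The documents do not support that. If the Protocol 14.1.2 remark were taken to mean that nonsense mutations are worse than others, the mixed controls would do better than untreated nonsense-mutation boys, and the bias would run against the drug.

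**The 85-90% figure is not a fact about CINRG.** Correct. The protocol's share refers to boys with DMD in general, and CINRG's mix is not reported. The figure is conditional, although the majority statement tolerates large departures from it.

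**The SAP does not forbid genotype.** Also correct. The list of extracted items is not exclusive, and the list of possible extra criteria is open-ended. It would go too far to say that the mismatch cannot be corrected or shown. What can be said is that mutation class is not prespecified.

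**The stakes are low.** Largely right. The primary objective is safety, and the functional measures are secondary and descriptive. SAP 5 mentions p-values only as a possibility, for information. With no planned between-cohort test, a false-positive rate would have no basis.

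**A nonsense-mutation column has its own hazard.** Protocol 1 says that ataluren is available in Europe and Israel for patients older than 5 years with this genotype. A control entering at up to 5 and followed for 52 weeks can pass that age, so any ataluren exposure among controls would be expected in that column. The documents do not say whether CINRG follow-up overlapped with availability, or whether CINRG recorded mutation class. Both points shape the fix.

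**Conclusion.** The omission is confirmed: SAP 3.9 prespecifies mutation class neither for selection nor among the listed data, while Study 030 requires a nonsense mutation. If CINRG has the general DMD mix, about 85-90% of controls would belong to another class. The display may then mix genotype with drug effect, by an amount and in a direction that the documents leave unknown, and a reader of the planned tables could not tell.

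The conclusion rests on one assumption about CINRG's mix and makes no claim that outcomes differ by class. The consequence is limited by the descriptive nature of the comparison and its separation from the study report and submission package. It still merits a change, because the stated aim is to illustrate benefit and the remedy is inexpensive.

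**What to change.** Amend SAP 3.9 as follows:

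1. Add dystrophin mutation class to the CINRG data request, where CINRG recorded it.
2. Report its distribution in the selected comparator, with the number unknown.
3. Show nonsense-mutation controls in a separate column beside the all-mutation cohort, with any known ataluren exposure identified or excluded.
4. If too few qualify, or genotype is unavailable, state the number and label the display as not matched on genotype.

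The cost is one more requested variable and one more column, plus ataluren exposure information for the nonsense-mutation controls where it exists. The drawback is precision: the subset may hold only a handful of boys, and its intervals will be wide. Keeping the all-mutation column means that no control data are lost.

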3. STUDY OBJECTIVES AND ENDPOINTS

3.1. Study Objectives

The primary objective of this study is to evaluate the safety of ataluren as measured by type, frequency, severity, timing, and relationship to study drug of treatment emergent adverse events (TEAEs), laboratory abnormalities and electrocardiograms (ECGs).

There are 5 secondary objectives of the study, presented in the order from section 3.2 of the protocol:

- Evaluate the plasma pharmacokinetics (PK) of ataluren in subjects aged ≥ 2 to < 5 years old with nmDMD
- Assess proximal muscle function using timed function tests (TFTs)
- Assess change in physical function using the North Star Ambulatory Assessment (NSAA)
- Determine the effect of ataluren on weight, height, and body mass index (BMI)
- Assess the palatability of ataluren

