8. DEMOGRAPHICS AND OTHER BASELINE CHARACTERISTICS

8.1. Baseline Demographic Factors and Medical History

All subjects in the Safety Population will be included in summary of demographic information in Table 14.1.3 entitled *Demographics and Baseline Characteristics* (Safety Population). This table summarizes the subject population with respect to gender, age (years) at screening, race and ethnicity. Age will be reported in months and years and summarized with descriptive statistics: n, arithmetic mean, SD, median, range (*i.e.*, minimum and maximum values). The number and percent of each gender, race, and ethnicity category will be presented using counts and percentages. Race will be presented using the following categories:

- Caucasian or White
- Black or African American
- Asian
- American Indian or Alaska Native
- Native Hawaiian or other Pacific Islander
- Other

The supportive data for Table 14.1.3 are presented in Listing 16.2.4.1 entitled *Demographics and Subject Characteristics* (Safety Population). This listing will be sorted by subject number.

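### SAP 3.9 fixes only age for choosing CINRG controls, with a window that differs from enrolment, and plans no set adjustment for baseline function in the TFT and NSAA comparison

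*SAP*

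**What the plan says.** SAP 3.9 gives one firm rule for choosing controls: "subjects from the CINRG database will be selected based on ≥ 2 and ≤ 5 of age-match at study entry". The same upper limit of 5 inclusive is used there to describe Study 030's own subjects. Enrolment is narrower. Protocol 4.2 admits "Males ≥ 2 to < 5 years of age", and the SAP's objectives agree: "Evaluate the plasma pharmacokinetics (PK) of ataluren in subjects aged ≥ 2 to < 5 years old with nmDMD". SAP 3.2 repeats that range.

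Beyond age, SAP 3.9 says that extra criteria, with baseline TFTs and NSAA scores as examples in an open list, "maybe selected if significant differences in baseline demographics are observed between the CINRG cohort and the Study 030 population". It names no variables, no test and no person who decides. SAP 8.1 says that its demographics table "summarizes the subject population with respect to gender, age (years) at screening, race and ethnicity".

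On content, SAP 3.9 states: "The data extracted from the CINRG database will include demographics at study entry, and available Timed Function Test and North Star Ambulatory Assessment", at entry and at Weeks 28 and 52. The CINRG data are to be summarised in the same way as Study 030. For Study 030, SAP 10 and 10.1 specify observed values and changes from baseline, with only paired data in the TFT tables. On reporting, SAP 3.9 says: "These summaries will be kept separate from the study CSR". The CINRG data also stay out of the study databases and the submission package.

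**The concern.** Study 030 has a single arm, and CINRG is the only external comparator in either document. Its stated purpose is to illustrate clinical benefit on TFTs and the NSAA. For such a display the most important baseline variables are age and the starting value of the measure being compared. Age is controlled through a window that does not match enrolment. Starting function is controlled only at someone's discretion, after a trigger that, as worded, looks at demographics and not at function. Two cohorts that differ at entry on a TFT or on the NSAA could therefore be set side by side at Weeks 28 and 52 with no rule that takes the difference into account.

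**Working it through.** **The plan's own figures.** There are none to reproduce. SAP 3.9 gives no control number, matching tolerance, test or power, and Protocol 11.1 says that the sample size of 12 has no formal statistical basis. The check is therefore a reading of the text plus an illustration.

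**Step 1: what the trigger can see.** Of the four demographics in SAP 8.1, gender cannot differ, because both Study 030 and CINRG enrolled males only. Age, race and ethnicity remain. None is a function measure. On the literal wording, a difference in baseline TFT or NSAA alone triggers nothing. On a looser reading, where demographics means all baseline characteristics, the trigger could see function, but the action remains optional.

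**Step 2: what the descriptive tables already do.** Showing change from baseline subtracts each boy's starting value. Suppose that follow-up depends on baseline with slope b and that the cohorts differ at baseline by Δ. The between-cohort difference in mean change then carries an extra term (b − 1)·Δ, and the difference in mean observed values carries b·Δ. The change score is free of the imbalance only if b = 1 or Δ = 0. Analysis of covariance estimates b from the data instead of fixing it at 1. The documents give neither b nor Δ, so the size and sign of the term cannot be derived.

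**Step 3: how well a significance check would find an imbalance.** Inputs:
- 12 treated boys (Protocol 11.1; Protocol 5.1 says at least 12)
- two-sided 0.05, borrowed from the general convention in SAP 5
- a two-sample t-test on one function measure (assumed)
- a true imbalance of 0.5 SD (assumed)
- 30, 50 or 100 controls (assumed; SAP 3.9 gives only the CINRG total of more than 400 at all ages)

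The standard error in SD units is √(1/12 + 1/n), the noncentrality is 0.5 divided by it, and the degrees of freedom are 12 + n − 2.

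| Controls n | Standard error | Noncentrality | Critical t | Chance of p<0.05 |
|---|---|---|---|---|
| 30 | 0.342 | 1.46 | 2.021 | 0.298 |
| 50 | 0.322 | 1.56 | 2.000 | 0.334 |
| 100 | 0.306 | 1.64 | 1.982 | 0.368 |

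With unlimited controls the ceiling is Φ(0.5√12 − 1.96) + Φ(−0.5√12 − 1.96) = 0.4098 + 0.0001 = 0.410. The 12 treated boys set the limit. A half-SD imbalance would be missed more often than found, whatever the number of controls.

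**Step 4: whether a cut-off on the standardised difference would serve better.** With no true imbalance, the chance that the observed difference exceeds 0.2 SD is about 2[1 − Φ(0.2/SE)]. This is 0.56 for 30 controls and 0.51 for 100. A pass/fail limit of 0.2 would therefore be crossed by chance about half the time. Standardised differences are useful here as description only.

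**Step 5: the age window.** With exact age, the two windows differ only for a boy aged exactly 5.0 years at entry, so the effect is negligible. SAP 8.1 says "Age will be reported in months and years" for Study 030, while SAP 3.9 does not say how age is measured in CINRG. If it were completed years, boys up to the sixth birthday would qualify.

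**The case against.** The strongest reply is that the plan already shows what a reader needs. Both cohorts will have baseline values and changes from baseline in view, so any imbalance is visible and starting level is partly handled. That stands. A reader might infer from SAP 3.9 alone that an imbalance in function would go wholly unaddressed, but SAP 10 and 10.1 do not support that reading. What is missing is narrower: mandatory matching or a model-based adjustment.

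It can also be said that SAP 5 supplies a p<0.05 convention for all presentations, so it would be wrong to say that the SAP contains no threshold. That stands too, although the convention sits in a remark on optional, informational p-values and names no test or variables for SAP 3.9. The examples given there suggest that demographics may have been meant broadly. That is plausible, but the broad reading still obliges no action.

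On age, a reader might infer that a quarter of the controls would be too old. That figure is one of four year-groups. It needs age in completed years and an even spread of ages, neither of which the documents state. SAP 3.9 applies the same loose limit to Study 030's own boys and speaks of an age match, which points to a wording slip.

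A reader might also infer that controls will be picked after outcomes are seen. The documents do not say so: the SAP declares itself prospective and the trigger uses baseline data. The point is only that no sentence fixes the list first.

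**Conclusion.** The concern holds in a limited form and is minor. SAP 3.9 fixes controls by age alone, with an upper limit that contradicts Protocol 4.2 and SAP 3.1 and 3.2. It leaves baseline function to an optional step behind a trigger that, taken with SAP 8.1, does not include function. Applied to one function measure, a p<0.05 check would find a 0.5 SD imbalance about 30% to 37% of the time, and at most 41%. These rates rest on the assumed test, imbalance and 30 to 100 controls; only the 12 treated boys come from the documents.

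The primary safety analysis and the PK analysis are untouched, and no protocol endpoint uses CINRG. A reader might infer that the comparison favours ataluren. The documents do not support that, because neither the direction nor the size of any bias can be derived from them. The age contradiction is certain as text and negligible in effect if exact age is used.

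**What to change.** Change SAP 3.9 in three places.

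(a) Write the age range as exact age at study entry, 2.0 to under 5.0 years, in both places where the range appears.

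(b) Replace the optional, significance-triggered sentence with one rule. Alongside the descriptive summaries, report the Week 28 and Week 52 differences between cohorts in each TFT and the NSAA, adjusted by ANCOVA for age and the baseline value of that outcome, among boys with baseline and follow-up values. Show baseline standardised differences as description, with no cut-off.

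(c) State that the control list is fixed from baseline data before Week 28 and Week 52 outcomes are compared.

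Age and available baseline TFT and NSAA are already in the planned extract, so no new data are needed. The cost is a little more analysis, the loss of boys who lack a baseline or follow-up value, and wide intervals. Before any gain from covariates, the 95% half-width is 2.021 × 0.342 = 0.69 SD with 30 controls and 1.982 × 0.306 = 0.61 SD with 100. The adjusted results should be presented as estimates with that imprecision in view, not as tests of benefit.
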